10.5. Appendix 5: Genetics

Use/Analysis of DNA

- Genetic variation may impact a participant's response to study intervention, susceptibility to, and severity and progression of disease. Therefore, where local regulations and IRBs/ECs allow, a blood sample will be collected for DNA analysis.
- The scope of the genetic research may be narrow (eg, 1 or more candidate genes) or broad (eg, the entire genome), as appropriate to the scientific question under investigation.
- The samples may be analyzed as part of a multistudy assessment of genetic factors involved in the response to zavege pant or study interventions of this class to understand treatments for the disease(s) under study or the disease(s) themselves.
- The results of genetic analyses may be reported in the CSR or in a separate study summary, or may be used for internal decision making without being included in a study report.
- The sponsor will store the DNA samples in a secure storage space with adequate measures to protect confidentiality.
- The samples will be retained as indicated:
- Retained samples will be stored indefinitely or for another period as per local requirements.
- Participants may withdraw their consent for the storage and/or use of their Retained Research Samples at any time by making a request to the investigator; in this case, any remaining material will be destroyed. Data already generated from the samples will be retained to protect the integrity of existing analyses.
- Samples for genetic research will be labeled with a code. The key between the code and the participant's personally identifying information (eg, name, address) will be held securely at the study site.

10.6. Appendix 6: Liver Safety: Suggested Actions and Follow-Up Assessments

Potential Cases of Drug-Induced Liver Injury

Humans exposed to a drug who show no sign of liver injury (as determined by elevations in transaminases) are termed “tolerators,” while those who show transient liver injury but adapt are termed “adaptors.” In some participants, transaminase elevations are a harbinger of a more serious potential outcome. These participants fail to adapt and therefore are “susceptible” to progressive and serious liver injury, commonly referred to as DILI. Participants who experience a transaminase elevation above $3 \times$ ULN should be monitored more frequently to determine if they are “adaptors” or are “susceptible.”

In the majority of DILI cases, elevations in AST and/or ALT precede T bili elevations ($>2 \times$ ULN) by several days or weeks. The increase in T bili typically occurs while AST/ALT is/are still elevated above $3 \times$ ULN (ie, AST/ALT and T bili values will be elevated within the same laboratory sample). In rare instances, by the time T bili elevations are detected, AST/ALT values might have decreased. This occurrence is still regarded as a potential DILI. Therefore, abnormal elevations in either AST OR ALT in addition to T bili that meet the criteria outlined below are considered potential DILI (assessed per Hy’s law criteria) cases and should always be considered important medical events, even before all other possible causes of liver injury have been excluded.

The threshold of laboratory abnormalities for a potential DILI case depends on the participant’s individual baseline values and underlying conditions. Participants who present with the following laboratory abnormalities should be evaluated further as potential DILI (Hy’s law) cases to definitively determine the etiology of the abnormal laboratory values:

- Participants with AST/ALT and T bili baseline values within the normal range who subsequently present with AST OR ALT values $\geq 3 \times$ ULN AND a T bili value $\geq 2 \times$ ULN with no evidence of hemolysis and an alkaline phosphatase value $< 2 \times$ ULN or not available.
- For participants with baseline AST **OR** ALT **OR** T bili values above the ULN, the following threshold values are used in the definition mentioned above, as needed, depending on which values are above the ULN at baseline:
 - Preexisting AST or ALT baseline values above the normal range: AST or ALT values ≥ 2 times the baseline values AND $\geq 3 \times$ ULN; or $\geq 8 \times$ ULN (whichever is smaller).
 - Preexisting values of T bili above the normal range: T bili level increased from baseline value by an amount of $\geq 1 \times$ ULN **or** if the value reaches $\geq 3 \times$ ULN (whichever is smaller).

Rises in AST/ALT and T bili separated by more than a few weeks should be assessed individually based on clinical judgment; any case where uncertainty remains as to whether it represents a potential Hy’s law case should be reviewed with the sponsor.

The participant should return to the investigator site and be evaluated as soon as possible, preferably within 48 hours from awareness of the abnormal results. This evaluation should include laboratory tests, detailed history, and physical assessment.

In addition to repeating measurements of AST and ALT and T bili for suspected Hy's law cases, additional laboratory tests should include albumin, CK, direct and indirect bilirubin, GGT, PT/INR, eosinophils (%), and alkaline phosphatase. Consideration should also be given to drawing a separate tube of clotted blood and an anticoagulated tube of blood for further testing, as needed, for further contemporaneous analyses at the time of the recognized initial abnormalities to determine etiology. A detailed history, including relevant information, such as review of ethanol, acetaminophen/paracetamol (either by itself or as a coformulated product in prescription or over-the-counter medications), recreational drug, or supplement (herbal) use and consumption, family history, sexual history, travel history, history of contact with a jaundiced person, surgery, blood transfusion, history of liver or allergic disease, and potential occupational exposure to chemicals, should be collected. Further testing for acute hepatitis A, B, C, D, and E infection, total bile acids, liver imaging (eg, biliary tract), and collection of serum samples for acetaminophen/paracetamol drug and/or protein adduct levels may be warranted.

All cases demonstrated on repeat testing as meeting the laboratory criteria of AST/ALT and T bili elevation defined above should be considered potential DILI (Hy's law) cases if no other reason for the LFT abnormalities has yet been found. **Such potential DILI (Hy's law) cases are to be reported as SAEs, irrespective of availability of all the results of the investigations performed to determine etiology of the LFT abnormalities.**

A potential DILI (Hy's law) case becomes a confirmed case only after all results of reasonable investigations have been received and have excluded an alternative etiology.

10.7. Appendix 7: Kidney Safety: Monitoring Guidelines

10.7.1. Laboratory Assessment of Change in Kidney Function and Detection of Kidney Injury

Standard kidney safety monitoring requires assessment of baseline and postbaseline Screat measurement to estimate kidney function [Screat-based eGFR] or creatinine clearance [eCrCl]). Obtaining Screening or Baseline Scys and postbaseline reflex Scys (if confirmed Screat increase ≥ 0.3 mg/dL) makes it feasible to distinguish AKI from DICI. If Screat increase is confirmed after baseline, then reflex measurement of Scys is indicated.

ADULTS: Currently, 2021 CKD-EPI eGFR equations (Screat only-based and combined Screat plus Scys-based) are valid for use in adults only. At baseline Screat and Scys values are needed to calculate 2021 CKD-EPI eGFR by Screat only-based equation (see Table 10.7.2.1.) and by combined Screat plus Scys-based equation. When post-baseline Screat increase ≥ 0.3 mg/dL is confirmed, then reflex Scys measurement is needed to enable post-baseline comparison of eGFR changes (Screat only-based eGFR and combined Screat plus Scys eGFR).

10.7.2. Age-Specific Kidney Function Calculation Recommendations

10.7.2.1. Adults (18 Years and Above)—2021 CKD-EPI Equations

eGFR (mL/min/1.73m²)³⁹

2021 CKD-EPI Screat Only	Screat (mg/dL)	Scys (mg/L)	Recommended eGFR Equation
Female	if ≤ 0.7	NA	$eGFR = 143 \times (\text{Screat}/0.7)^{-0.241} \times (0.9938)^{\text{Age}}$
Female	if > 0.7	NA	$eGFR = 143 \times (\text{Screat}/0.7)^{-1.200} \times (0.9938)^{\text{Age}}$
Male	if ≤ 0.9	NA	$eGFR = 142 \times (\text{Screat}/0.9)^{-0.302} \times (0.9938)^{\text{Age}}$
Male	if > 0.9	NA	$eGFR = 142 \times (\text{Screat}/0.9)^{-1.200} \times (0.9938)^{\text{Age}}$
2021 CKD-EPI Screat-Scys Combined	Screat (mg/dL)	Scys (mg/L)	Recommended eGFR Equation
Female	if ≤ 0.7	if ≤ 0.8	$eGFR = 130 \times (\text{Screat}/0.7)^{-0.219} \times (\text{Scys}/0.8)^{-0.323} \times (0.9961)^{\text{Age}}$
Female	if ≤ 0.7	if > 0.8	$eGFR = 130 \times (\text{Screat}/0.7)^{-0.219} \times (\text{Scys}/0.8)^{-0.778} \times (0.9961)^{\text{Age}}$
Female	if > 0.7	if ≤ 0.8	$eGFR = 130 \times (\text{Screat}/0.7)^{-0.544} \times (\text{Scys}/0.8)^{-0.323} \times (0.9961)^{\text{Age}}$
Female	if > 0.7	if > 0.8	$eGFR = 130 \times (\text{Screat}/0.7)^{-0.544} \times (\text{Scys}/0.8)^{-0.778} \times (0.9961)^{\text{Age}}$
Male	if ≤ 0.9	if ≤ 0.8	$eGFR = 135 \times (\text{Screat}/0.9)^{-0.144} \times (\text{Scys}/0.8)^{-0.323} \times (0.9961)^{\text{Age}}$
Male	if ≤ 0.9	if > 0.8	$eGFR = 135 \times (\text{Screat}/0.9)^{-0.144} \times (\text{Scys}/0.8)^{-0.778} \times (0.9961)^{\text{Age}}$
Male	if > 0.9	if ≤ 0.8	$eGFR = 135 \times (\text{Screat}/0.9)^{-0.544} \times (\text{Scys}/0.8)^{-0.323} \times (0.9961)^{\text{Age}}$
Male	if > 0.9	if > 0.8	$eGFR = 135 \times (\text{Screat}/0.9)^{-0.544} \times (\text{Scys}/0.8)^{-0.778} \times (0.9961)^{\text{Age}}$

10.7.3. Kidney Function Calculation Tools

The sponsor has provided the following resources to investigational sites when required to calculate age-specific kidney function at Screening, Baseline, and post-Baseline visits. Site calculations of kidney function can be performed manually, using the age appropriate formulae (see Section 10.7.2) and can use recommended online kidney function calculators to reduce the likelihood of a calculation error.

The United States National Kidney Foundation Online Calculators.

- Adults (18 years and above) - 2021 CKD-EPI Creatinine Online Calculator (eGFR):
https://www.kidney.org/professionals/KDOQI/gfr_calculator

Investigational sites are responsible to ensure that the accurate age-specific equation is selected and that the correct units for serum creatinine (mg/dL only), serum cystatin C (mg/L only), total body weight (kg only), and age (years). Investigators are expected to (i) review and confirm correctness of the kidney function calculation results and (ii) evaluate the calculated value within the context of historical information available to them in the participant's medical record. Investigators are responsible for the clinical oversight of the participant eligibility process, kidney function calculation, and dose selection and adjustments per study protocol. Investigators are encouraged to direct questions or uncertainties regarding kidney function and dosing to the Pfizer Clinical Team and Medical Monitor, if needed.

10.7.4. Adverse Event Grading for Kidney Safety Laboratory Abnormalities

AE grading for decline in kidney function (ie, eGFR or eCrCl) will be according to Kidney disease: Improving Global Outcomes (KDIGO) criteria.

NON-ONCOLOGY Studies					
KDIGO criteria	Grade 1	Grade 2	Grade 3	Grade 4	Grade 5
Decreased Kidney Function due to either Acute or Chronic Kidney Injury	eGFR \geq 90 mL/min/1.73m ² OR eCrCl \geq 90 mL/min	eGFR \geq 60 to 89 mL/min/1.73m ² OR eCrCl \geq 60 to 89 mL/min	eGFR 30 to 59 mL/min/1.73m ² OR eCrCl 30 to 59 mL/min	eGFR 15 to 29 mL/min/1.73m ² OR eCrCl 15 to 29 mL/min	eGFR <15 mL/min/1.73m ² OR eCrCl <15 mL/min OR dialysis indicated
Albuminuria	Albuminuria <30 mg/g OR <3 mg/mmol	Albuminuria 30 to 300 mg/g OR 3 to 30 mg/mmol	Albuminuria >300 mg/gm OR <3 mg/mmol		

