7. DISCONTINUATION OF STUDY INTERVENTION AND PARTICIPANT DISCONTINUATION/WITHDRAWAL

7.1. Discontinuation of Study Intervention

It may be necessary for a participant to permanently discontinue study intervention. Reasons for permanent discontinuation of study intervention include the following:

- AE (including Grade 3 severity or greater and considered by the investigator to be related to study intervention);
- SAE considered by the investigator to be related to study intervention;

- Requirement for prohibited concomitant medication;
- Study terminated by sponsor;
- Withdrawal by participant or legally authorized representative.

Discontinuation of study intervention does not represent withdrawal from the study. If study intervention is permanently discontinued, the participant should remain in the study to be evaluated for subsequent scheduled assessments. See the [SoA](#) for data to be collected at the time of discontinuation of study intervention and follow-up for any further evaluations that need to be completed.

In the event of discontinuation of study intervention, it must be documented on the appropriate CRF/in the medical records whether the participant is discontinuing further receipt of study intervention or also from study procedures, further study follow-up, and/or future collection of additional information.

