7.1.1. Potential Cases of Acute Kidney Injury

Participants exposed to IMP demonstrating transient or sustained increase in Screat (with decrease in Screat-based eGFR or eCrCL) require expedited evaluation to differentiate AKI from DICI. DICI is defined as transporter-mediated effect related to altered renal tubular creatinine handling without histological injury.

AKI may be due to one or more types of injury, including DIKI. Differentiation of DIKI from other causes of AKI and from DICI may require clinical, radiographic, histopathologic, and laboratory assessments, as well as nephrology consultation.

Follow-up Assessments

The participant should return to the site for evaluation as soon as possible, preferably within 48 hours of awareness of the abnormal results.

Evaluation should include physical examination, laboratory tests, detailed medical and surgical history, review of all medications (including recreational drugs and supplements [herbal]), family history, sexual history, travel history, blood transfusion, and potential occupational exposure to chemicals.

Laboratory assessments should include simultaneous serum cystatin C (Scys) and serum creatinine (Screat) tests. Estimates of eGFR, eCrCl and Screat-based eGFR and combined Screat-Scys-based eGFR should also be derived using the appropriate equation described in [Appendix 7](#).

Assessments of urine albumin-to-creatinine ratio or urine volume may also be performed as appropriate.

If appropriate, nephrology consultation may be recommended to facilitate differentiation of renal parenchymal disease, pre-renal azotemia, and post-renal obstruction.

Differentiating Acute Kidney Injury from DIKI

A confirmed Screat increase is defined as:

- (i) ≥ 0.3 mg/dL (≥ 26.5 μ mol/L) within 48 hours OR
- (ii) confirmed Screat increase ≥ 1.5 times baseline (known or suspected to have occurred within the prior 7 days).

Based on the assessments performed, suspected AKI (including DIKI) may be differentiated from DIKI as follows.

Adult participants

	AKI (including DIKI) Any one of the below	DICI
Scys & Screat	Simultaneous, confirmed serum cystatin C (Scys) increase and confirmed Screat increase	Confirmed Screat increase without confirmed increase in reflex Scys AND Confirmed Screat-based eGFR decrease without confirmed combined Screat-Scys-based eGFR decrease.
eGFR	Decrease in Screat-based eGFR and combined Screat-Scys-based eGFR (when available)	

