Albuminuria or proteinuria	Confirmed albuminuria increase (see Appendix 7 for Grades A1 to A3 quantitation)	
Urine volume	Urine volume <0.5 mL/kg/h for 6 consecutive hours	

Regardless of the presence or absence of increase in Screat, DIKI and other causes of AKI may be suspected if either there is new-onset or worsening albuminuria or proteinuria are detected.

All confirmed cases of clinically relevant decrease in kidney function should be considered potential cases of DIKI if no other reason for the kidney function abnormalities has been found.

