10.2. Appendix 2: Clinical Laboratory Tests

The following safety laboratory tests will be performed at times defined in the **SoA** section of this protocol. Additional laboratory results may be reported on these samples as a result of the method of analysis or the type of analyzer used by the clinical laboratory, or as derived from calculated values. These additional tests would not require additional collection of blood. Unscheduled clinical laboratory measurements may be obtained at any time during the study to assess any perceived safety issues.

Table 4. Protocol-Required Laboratory Assessments

Hematology	Chemistry	Urinalysis	Other
Hemoglobin	BUN	Local dipstick: pH	
Hematocrit	Creatinine	Glucose (qual)	Pregnancy test (β -hCG)
RBC count	Cystatin C ^a	Protein (qual)	Urine drug screening ^d
Platelet count	eGFR, eCrCl ^b	Blood (qual)	Urine cotinine
WBC count	Glucose (fasting)	Ketones	
Total neutrophils (Abs)	Calcium	Nitrites	At screening:
Eosinophils (Abs)	Sodium	Leukocyte esterase	
• FSH^c• HBcAb• HBsAb^f• HBsAg• HCVAb• HIV
Monocytes (Abs)	Potassium	Laboratory: Microscopy and culture ^e	
Basophils (Abs)	Chloride		
Lymphocytes (Abs)	Total CO ₂ (bicarbonate)		
	AST, ALT		
	Total bilirubin		
	Alkaline phosphatase		
	Uric acid		
	Albumin		
	Total protein		
	For suspected DICI/DIKI: Creatinine (Screat) Cystatin C ^a (Scys) eGFR (Screat only and combined Screat+Scys) eCrCl ^b		
	Urine albumin-to-creatinine-ratio (UACR)		

a. Cystatin C (Scys): Screening or Baseline Scys is recommended to help differentiate post-baseline DIKI from DICI. Post-baseline, Scys is measured if and only if serum creatinine increase post-baseline is observed (see [Section 7.1.1](#)).

b. Screening and Baseline eGFR or eCrCl is measured with Screat-based formula. Age-specific kidney function calculation (see [Section 10.7.2](#)) is recommended to assess presence or absence of post-baseline change in kidney function.

c. Only if UTI is suspected and urine dipstick is positive for nitrites or leukocyte esterase or both.

d. The minimum requirement for drug screening includes cocaine, THC, opiates/opioids, benzodiazepines, and amphetamines (others are site- and study-specific).

e. For confirmation of postmenopausal status only in females <60 years old and not using hormonal or HRT only.

f. This is a reflex test. HBsAb to be run if HBsAg and/or HBcAb are positive.

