3.5.2. Laboratory Data

Safety laboratory tests will be performed as described in the protocol. To determine if there are any clinically significant laboratory abnormalities, the haematological, clinical chemistry (serum) and urinalysis safety tests will be assessed against the criteria specified in the sponsor reporting standards. The assessment will not take into account whether each participant’s baseline test result is within or outside the laboratory reference range for the particular laboratory parameter.

The baseline measurement is the predose measurement on Day -1.

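### The Grade 3 albuminuria limit in protocol Section 10.7.4 is printed as <3 mg/mmol, the same as Grade 1; it should read >30 mg/mmol

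*Protocol*

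**What the plan says.** The albuminuria row of the table in protocol Section 10.7.4 gives each limit in two units joined by OR:

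- Grade 1: "Albuminuria <30 mg/g OR <3 mg/mmol"
- Grade 2: "Albuminuria 30 to 300 mg/g OR 3 to 30 mg/mmol"
- Grade 3: "Albuminuria >300 mg/gm OR <3 mg/mmol"

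The albuminuria row has no Grade 4 or Grade 5 entry.

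The row is used elsewhere. The adult table in Section 7.1.1 lists among its criteria for acute kidney injury (AKI) "Confirmed albuminuria increase (see Appendix 7 for Grades A1 to A3 quantitation". Section 7.1 lists as a reason for permanent discontinuation of study intervention "AE (including Grade 3 severity or greater and considered by the investigator to be related to study intervention".

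Two other places limit how often the row would be consulted. In Table 4 (Appendix 2), "Urine albumin-to-creatinine-ratio (UACR" appears under the tests for suspected drug-induced creatinine increase (DICI) or drug-induced kidney injury (DIKI). Section 7.1.1 makes the test optional: "Assessments of urine albumin-to-creatinine ratio or urine volume may also be performed as appropriate".

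**The concern.** A severity scale should rise, and each value should fall in one grade. Here the top grade carries the bottom grade's mg/mmol limit. Because the two units are joined by OR, a normal result reported in mg/mmol satisfies Grade 1 and Grade 3 together, while a markedly raised result satisfies no mg/mmol limit.

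What is at stake is clear safety grading during the work-up of a suspected kidney injury. That is when Section 7.1.1 directs the investigator to Appendix 7. General AE intensity in Section 10.3.3 is mild, moderate or severe, and the Section 10.7.4 table is the only one in the protocol that defines numbered Grades 1 to 5. The Grade 3 wording in the discontinuation rule therefore has this table as its only numerical definition for a kidney finding.

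**Working it through.** **Inputs.** The three cells come from Section 10.7.4. The creatinine conversion comes from Section 7.1.1, where a rise of 0.3 mg/dL is equated with 26.5 µmol/L. No outside figure is needed.

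**Step 1: can the printed Grade 3 limit be reproduced from the row?** The ratio of mg/g to mg/mmol in the other cells is:

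- Grade 1 limit and lower end of Grade 2: 30 / 3 = 10
- Upper end of Grade 2: 300 / 30 = 10

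Applied to the Grade 3 limit of 300 mg/g: 300 / 10 = 30, so the pair is >30 mg/mmol. The printed <3 mg/mmol corresponds to 3 × 10 = 30, that is <30 mg/g, which is Grade 1. The printed figure is not reproduced, and both the direction of the sign and the number differ.

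**Step 2: check with the protocol's own creatinine conversion.**

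- 0.3 mg/dL = 3 mg/L, and 26.5 µmol/L = 0.0265 mmol/L
- 1 mmol creatinine = 3 / 0.0265 = 113.2 mg
- 1 mg/mmol = 1000 / 113.2 = 8.83 mg/g
- 3 mg/mmol = 26.5 mg/g; 30 mg/mmol = 265 mg/g; 300 mg/g = 300 / 8.83 = about 34 mg/mmol

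On this exact conversion too, <3 mg/mmol lies wholly inside Grade 1 and cannot be an alternative statement of >300 mg/g.

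**Step 3: grade some values.**

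| UACR, mg/mmol | Same value, mg/g | As printed, mg/mmol limits only | As printed, either unit | Corrected, mg/mmol limits only |
|---|---|---|---|---|
| 2 | 17.7 | 1 and 3 | 1 and 3 | 1 |
| 10 | 88.3 | 2 | 2 | 2 |
| 31 | 274 | none | 2 | 3 |
| 40 | 353 | none | 3 | 3 |

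The double grade holds for every value below 3 mg/mmol, and converting to mg/g does not remove it. For values above 30 mg/mmol, conversion does recover a grade: Grade 2 up to about 34 mg/mmol and Grade 3 beyond. With the corrected limit, each value falls in exactly one grade on the mg/mmol scale.

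The value 31 mg/mmol is Grade 2 in mg/g and Grade 3 under the corrected mg/mmol limit. This comes from the row's 10:1 rounding of a ratio that is really 8.83:1. It affects only the bands 3 to 3.4 and 30 to 34 mg/mmol (30 / 8.83 = 3.4). It is a feature of rounded limits and separate from the misprint.

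**The case against.** The strongest reply is that nobody would be misled. To call a normal UACR Grade 3, a reader would have to ignore >300 in the same cell, the identical <3 under Grade 1, and the ascending Grade 2 range. Section 10.7.4 also names KDIGO as the source of the criteria, so the intent is clear.

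The consequences are limited as well:

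- Routine urinalysis measures only dipstick protein, so no scheduled test is graded by this row.
- The AKI criterion is a confirmed increase in albuminuria, which a normal value does not meet. Neither the AKI nor the DICI classification uses Grade 3.
- SAP Section 3.5.2 states that "urinalysis safety tests will be assessed against the criteria specified in the sponsor reporting standards", and the SAP names no analysis based on these grades.
- Discontinuation needs an AE judged related, and a UACR below 3 mg/mmol would not become an AE by itself. There are two fixed doses 24 hours apart, and the only scheduled safety laboratory sample after dosing is drawn just before the second. A follow-up UACR would usually come too late to change dosing.
- The protocol does not state the unit in which UACR will be reported. Appendix 7 asks for serum creatinine in mg/dL only, so the mg/mmol limit may never be used at this single centre.

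All of this stands as a statement of small reach. None of it makes the cell right. The table offers the two units as alternatives, nothing else in the protocol or SAP corrects the limit, and a safety threshold should not rely on the reader to repair it.

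**Conclusion.** The concern holds. The Grade 3 albuminuria limit in mg/mmol is wrong as written, and the row itself shows that >30 mg/mmol was meant. As printed, every UACR below 3 mg/mmol meets Grades 1 and 3 together, and every UACR above 30 mg/mmol meets no mg/mmol limit. The mg/g limits are consistent.

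This is an internal contradiction in an appendix table with limited practical effect. It matters only if a suspected kidney event leads to a UACR that is graded against the mg/mmol limits. The PK comparison, the sample size and the planned safety summaries are untouched.

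The conclusion assumes that the cell in the source protocol reads as quoted. A character error in the PDF text cannot be wholly excluded. It is unlikely, because turning >30 into <3 takes both a reversed sign and a lost digit, while >300 in the same cell is intact.

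**What to change.** In protocol Section 10.7.4, change the Grade 3 albuminuria cell to **>300 mg/g OR >30 mg/mmol**. This also brings the unit mg/gm into line with the mg/g used in the other two cells. Confirm the cell against the source document when making the edit.

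The cost is one table cell in Appendix 7. No assessment, analysis or SAP text changes.
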